#### **11.1.1.3. Statistical Methods**

A two-sided 95% confidence interval will be constructed using exact (Clopper-Pearson) method to estimate the SADE rate at 30 days post procedure for lithotripsy cohort and the SADE rate at 3-month post procedure for BPH cohort.

#### **11.1.2. Primary Efficacy Endpoints**

Lithotripsy procedure cohort: Stone clearance assessed by stone free rates (SFR) at 1 month follow-up. SFR is defined as clinically nonsignificant, non-obstructive residual fragments of  $\leq$  3 mm, asymptomatic and no auxiliary procedures performed between the final Flexiva Pulse holmium laser lithotripsy procedure and the 1 month follow-up.

BPH procedure cohort: Improvement in BPH symptoms from Baseline as measured by favorable change in International Prostate Symptom Score (IPSS) at 3-month follow-up.

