### **10.8. Post Lithotripsy/HoLEP Procedure Follow-up Visits**

#### **10.8.1. All SOC Follow-up Visits within 60 days post discharge from final Flexiva Pulse holmium laser Lithotripsy procedure**

For any follow-up visit(s) that occurs within 60 days post discharge from final Flexiva Pulse holmium laser lithotripsy procedure per site's standard of care, the following assessments will be performed and data points collected if available:

- Imaging Study Report: Computed Tomography (CT) or x-ray or ultrasound of kidneys, ureters, and bladder (KUB). **At least one imaging study report is required within 60 days of discharge for stone free rate assessment.**
- Assessment of adverse events
- COVID-19 assessment: prior diagnosis, test result, vaccination status
- Study Exit at last follow-up visit within 60 days post discharge

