### **10.9. Unscheduled Visit**

Subjects may have additional visits (other than the study visits specified above), that are unplanned visits and are considered as unscheduled visits. Some examples of these visits may include a visit for a change in symptoms or to check on a medical event that could not be resolved during one of the scheduled study visits.

If an unscheduled visit occurs, the following information will be collected:

- Assessment of adverse events
- COVID-19 assessment: prior diagnosis, test result, vaccination status (if available)

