#### **11.1.2.2. Statistical Methods**

Lithotripsy procedure cohort: The proportion of subjects who achieved stone clearance at 1 month follow-up post lithotripsy procedure will be calculated.

BPH procedure cohort: The change of IPSS total score at 3-month and 6-month post BPH procedure from baseline will be summarized using descriptive statistics. The same analysis will be performed for subjects with and without catheter at baseline if applicable.

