#### ***14.5. General Data Protection Regulations (GDPR)***

Data collected from clinical trial data subjects are considered “personal data” (including sensitive personal data in some cases). The protection of clinical trial subject personal data and compliance with privacy, data protection laws and regulations are of critical importance to BSC. Data collection has been carefully considered for this study and has been restricted to the strict essentials with a clear, specific and detailed purpose to mitigate the risk and the impact of data breach and to comply with data privacy laws (including but not limited to HIPAA and GDPR). Section 10 of the protocol defines the data that need to be collected to fulfill the objectives of the clinical study.

Personal data collected by BSC includes, but is not limited to:

- Geographic data (site name)
- Important Dates
  - Informed consent date
  - Age at the time of study enrollment
  - Procedure date
  - Adverse event start/end date
  - Hospitalization admission/discharge date
  - Subject visit dates

The purposes of the personal data processing will be carefully defined within the informed consent form. Personal data will not be used for a purpose other than the one stated in the informed consent provided to the subjects. Personal data shall not be disclosed, made available,

or otherwise used, processed, transferred, or stored for purposes other than those specified in the informed consent form, except:

- with the consent of the data subject; or
- processing is necessary for compliance with a legal obligation.

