## 17. Safety Reporting

### 17.1. *Reportable Events by investigational site to BSC*

It is the responsibility of the investigator to assess and report to BSC any event which occurs in any of following categories, from the time of Lithotripsy/HoLEP procedure to the end of the study:

- Serious Adverse Device Effects (SADEs)
- Procedure Related Serious Adverse Events (SAEs)
- Fatal Serious Adverse Events (SAEs)
- Adverse Device Effects (ADEs)
- Procedure Related Adverse Events (AEs)
- Device Deficiencies (including BSC devices used during the procedure)

When possible, the medical diagnosis should be reported as the Event Term instead of individual symptoms.

If it is unclear whether or not an event fits one of the above categories, or if the event cannot be isolated from the device or procedure, it should be submitted as an adverse event and/or device deficiency.

Any reportable event must be recorded in the eCRF.

The Investigator or designee is responsible for updating the eCRF with new and/or updated information in relation to the already reported event as soon as he/she becomes aware.

Underlying diseases and chronic conditions are not reported as AEs unless there is an increase in severity or frequency during the course of the investigation. Death should not be recorded as an AE, but should only be reflected as an outcome of one (1) specific SAE (see **Table 17.2-1** for AE definitions).

Refer to Instructions for Use for the known risks associated with the commercial device(s).

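### Two conditions of the stone-free endpoint, no symptoms and no auxiliary procedure, have no dedicated data item and no derivation rule, and subjects exited for a non-Flexiva lithotripsy may leave the denominator

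*Combined protocol and SAP*

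**What the plan says.** Section 11.1.2, with the same definition in the Synopsis and Table 6-1, makes stone-free status a composite. Any residual fragments must be at most 3 mm, clinically insignificant and non-obstructive, and the subject must be "asymptomatic and no auxiliary procedures performed between the final Flexiva Pulse holmium laser lithotripsy procedure and the 1 month follow-up". On analysis, section 11.1.2.2 says only that "The proportion of subjects who achieved stone clearance at 1 month follow-up post lithotripsy procedure will be calculated".

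For standard-of-care visits in the 60 days after discharge, section 10.8.1 states that "the following assessments will be performed and data points collected if available". It then lists an imaging report, adverse events, COVID-19 status and study exit. One item is tied to the endpoint by name: "At least one imaging study report is required within 60 days of discharge for stone free rate assessment". Table 10.1-1 agrees, and it records medications only at baseline and discharge.

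On unscheduled visits, section 10.9 says: "Some examples of these visits may include a visit for a change in symptoms". It continues "If an unscheduled visit occurs, the following information will be collected", and the list holds adverse events and COVID-19 status only. Table 10.1-1 has no imaging mark in that column.

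Section 17.1 makes non-fatal adverse events reportable when they are related to the device or procedure, and adds: "Underlying diseases and chronic conditions are not reported as AEs unless there is an increase in severity or frequency". Sections 10.6 and 10.10 exit a subject whose additional lithotripsy does not use Flexiva Pulse fibers. Section 11.3 restricts analyses to available cases unless otherwise specified.

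**The concern.** This is the primary efficacy endpoint of the lithotripsy cohort, and two of its conditions have no field of their own. The BPH cohort's primary endpoint, by contrast, has an IPSS row in Table 10.1-2. Section 14.5 says "Section 10 of the protocol defines the data that need to be collected to fulfill the objectives of the clinical study", so a reader would look to Section 10 for the source of both conditions and would not find it.

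A site can therefore follow the schedule exactly and still leave some failures unrecorded. The analyst cannot reliably recover symptom status afterwards. An absent adverse event form is not a record that the subject had no symptoms. The error on these conditions has one direction: a missed symptom or procedure turns a failure into a success, or removes a failure from the denominator. Any effect would carry into the staged and unilateral/bilateral subgroups in section 11.3.4.

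**Working it through.** **1. The plan's own figure.** The only sizing calculation (section 11.1.1.2) concerns serious adverse device effects. The Clopper-Pearson width with n = 90 and x = np is 8.40 points at 3% and 10.23 points at 5%, and 90/0.9 = 100. The stated 8.4%, 10.2% and 100 reproduce. None of this bears on the stone-free rate, for which the plan gives no expected value.

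**2. Where each condition could be recorded.**

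| Condition | Available record | Without a stated place |
|---|---|---|
| Fragment size, no obstruction | Imaging report from follow-up visits, at least one required | Scan taken at an unscheduled visit |
| Asymptomatic | Adverse event assessment at every follow-up and unscheduled visit | Unchanged stone symptoms; symptoms judged unrelated; a positive record of no symptoms |
| Repeat Flexiva lithotripsy | Own procedure and discharge forms (Table 10.1-1, footnote 2) | Nothing: the window runs from the final Flexiva procedure, so it restarts |
| Lithotripsy without Flexiva | Study exit (10.6, 10.10) | How the subject is scored |
| Other auxiliary procedure | Treatment entry on the adverse event form (Table 17.4-1), if there is a reportable event | One done without a reportable event, including at another hospital |

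**3. Missed failures.** Let S be the scan-clear rate, q the share of scan-clear subjects who had a disqualifying symptom or procedure, and c the fraction of these captured by other records. Overstatement = S × q × (1 − c). All inputs are assumed: S = 70% to 90%, q = 2% to 15%.

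- c = 0: from 0.70 × 0.02 = 1.4 points to 0.90 × 0.15 = 13.5 points. At S = 80% and q = 5%, 80% is reported instead of 76%.
- c = 0.5: 0.7 to 6.75 points.
- c = 1: 0 points.

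**4. Exits for a non-Flexiva lithotripsy.** Let a subjects per 100 exit before 1 month, and let S = 80% (assumed) among the rest. If they are dropped, 80% is reported. If they are kept as failures, the rate is S × (100 − a)/100.

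| a | Kept as failures | Difference, S × a/100 |
|---|---|---|
| 2 | 78.4% | 1.6 points |
| 5 | 76.0% | 4.0 points |
| 10 | 72.0% | 8.0 points |

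Steps 3 and 4 are separate illustrations and should not be added. For scale, taking 90 evaluable subjects as an illustrative denominator, the exact 95% interval for 72/90 = 80% is 70.2% to 87.7%.

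**The case against.** A reader might infer that no visit captures symptoms or further procedures at all. The documents do not support that. Adverse events are assessed at the procedure, at discharge, and at every follow-up and unscheduled visit, and the form records treatment. Section 17.1 tells sites to submit events that are unclear or cannot be separated from the device or procedure, and Table 17.3-1 classes events of unassessable relationship as possibly related. Colic from a fragment within a month of laser treatment would often be caught this way. Further lithotripsy leaves a trace either on its own forms or as a study exit. This stands, and it makes the gap partial.

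A reader might also infer that the endpoint reduces to the scan alone. Section 10.8.1 makes imaging necessary, not sufficient, and no section says that the rate is decided on imaging only. The eCRFs and the adjudication charter are not part of the documents and may hold these fields. Section 19.2 provides for adjudication of important endpoints, although it does not name this one. Section 14.5 is a data-protection paragraph, and its own list includes hospitalization dates that Section 10 does not itemize. Table 10.1-1 likewise has no row for the fiber information that section 10.6 collects. A missing row is therefore not proof of a missing field.

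Finally, a demonstrated upward bias of some stated size would be too strong. The direction follows from the definition, but the size depends wholly on unknown rates and capture. These points limit severity. They do not supply a source or a derivation rule for the two conditions.

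**Conclusion.** The gap is real and limited. The plan names no dedicated item for symptom status or auxiliary procedures, lists no imaging at unscheduled visits, does not say how the composite is derived, and does not say how a subject exited for a non-Flexiva lithotripsy is scored. The indirect records leave three identifiable holes: unchanged stone symptoms, symptoms judged unrelated to device or procedure, and auxiliary procedures other than lithotripsy without a reportable event.

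The consequence is a risk of an overstated stone-free rate. Its size is unknown: zero if other records capture everything and exited subjects are retained as failures, and several points under the assumed inputs above. The exit illustration assumes that such a procedure counts as auxiliary, a term the plan does not define, and that exited subjects lack an evaluable 1-month result. Severity is moderate, because section 11.1.2.1 makes the endpoint descriptive and no decision threshold depends on it.

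**What to change.** - **Symptoms.** Add to Table 10.1-1 and section 10.8.1: *stone-related symptoms present at this visit (Y/N)*.
- **Auxiliary procedures.** Add to Table 10.1-1, sections 10.8.1 and 10.9, and Study Exit: *auxiliary stone procedure since final Flexiva procedure (Y/N, type, date, including other hospitals)*.
- **Imaging.** Mark the imaging report *if performed* in the Unscheduled Visit column.
- **Derivation, section 11.1.2.2.** State that the stone-free rate is derived from imaging plus these fields, with symptom status taken at the 1-month assessment. Symptoms that resolved earlier then do not count as failure, and the definition is not tightened. State that any auxiliary procedure in the window, including a non-Flexiva lithotripsy leading to exit before 1 month, is scored as not stone-free and kept in the denominator. Show the imaging-only rate alongside.

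If the eCRFs already hold these fields, citing them in Sections 10 and 11 and adding the scoring rule is enough.

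The cost is a small data-entry burden and a possibly lower reported rate. No visit or test is added, since only scans already performed would be collected.

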**Table 10.1-1: Data Collection Schedule - Lithotripsy Cohort**

Procedure/ Assessment	Screening	Baseline 	Lithotripsy Procedure 	Post Procedure Discharge 	Post final Flexiva Pulse holmium laser Lithotripsy Procedure Follow-up (FU) Visits	Unscheduled Visit
					All SOC FU visits within 2 months (60 days) of discharge	
Eligibility criteria	X					
Informed consent process, including informed consent signature date	X					
Demographics		X				
Medical history		X				
Physical examination, including weight and height		X				
Imaging Study Report		X			X 	
Medications		X		X		
Laboratory Blood Analysis for Lithotripsy Cohort: CBC, coagulation testing (PT, PTT, INR), serum creatinine, uric acid, CRP, BMP		X 				
Laboratory Urinalysis/Culture: Pregnancy Test and UTI		X				
Adverse Events assessment			X	X	X	X
Device Deficiency assessment			X	X		
COVID-19 Assessment		X 	X 	X 	X 	X 

X = required

 = If available = If additional Flexiva Fiber holmium laser lithotripsy procedure is performed, complete additional procedure and discharge CRF = Pregnancy test and urinalysis/culture must be completed within 30 days of procedure, and all other baseline data may be within 60 days = At least one imaging study report required within 60 days of discharge for stone free rate assessment

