#### **10.6. *Lithotripsy/HoLEP Procedure Visit***

Lithotripsy/HoLEP procedure is defined as the start time of sedation and/or anesthesia and includes the entirety of the holmium laser Lithotripsy or HoLEP procedure. The procedure will be performed by a trained physician and per the Flexiva Pulse Laser Fiber IFU.

It is recommended that surgeons perform a second evaluation at the time of the lithotripsy procedure to ensure all stones have been removed.

If multi-staged lithotripsy procedures are performed using the Flexiva Pulse Laser Fibers, then data will also be collected on the additional procedures. **If the additional lithotripsy procedure performed does not use the Flexiva Pulse Laser Fibers, then subject should be exited from the study at the time of the additional procedure.**

If subject is undergoing HoLEP and simultaneous holmium laser lithotripsy using Flexiva Pulse Laser Fibers to remove bladder calculi, data will also be collected on the lithotripsy procedure.

Baseline visit information may be collected on same day, prior to the Lithotripsy/HoLEP procedure.

After the Lithotripsy/HoLEP procedure, the following data will be collected:

- Procedure information and evaluation of applicable BSC devices used. It is recommended that User Feedback Evaluations are **completed within 1 week of procedure.**
- Fiber Information – type, size, number of fibers used, model of scope, number of passes per fiber, fiber fracture, fiber deflection, if fiber was stripped/cleaved
- Fiber Performance – fiber tip degradation
- Assessment of adverse events and device deficiencies
- COVID-19 assessment: prior diagnosis, test result, vaccination status (if available)

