### **10.10. *Study Completion***

Each subject in the Lithotripsy cohort will be followed up to 60 days post discharge from final Flexiva Pulse holmium laser Lithotripsy procedure per site's SOC. Each subject in the BPH cohort will be followed up to 6 months (180 days + 60 days) post discharge from HoLEP procedure per site's SOC. All subjects completing the last follow-up visit per site's SOC and their respective cohorts, will be considered to have completed the study. Subjects with any ongoing Adverse Events at the end of the study should be followed per institutions' standard of care.

If subject in the Lithotripsy cohort is undergoing a multi-staged lithotripsy procedure that does not use the Flexiva Pulse Laser Fibers, then subject should be exited from the study at the time of the additional procedure.

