## **11.3. *Data Analyses***

The analyses will include the available cases only unless specified otherwise. Presentation of summary statistics for continuous variables will include N, mean, median, standard deviation, minimum, and maximum values. For categorical variables, the number and percentage under each category will be presented

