#### 11.3.4. **Subgroup Analyses**

Primary safety and efficacy endpoints will be evaluated for subjects in the subgroups listed below if applicable:

- \* With and without staged procedure in the Lithotripsy procedure cohort.
- \* Unilateral and bilateral procedures in the Lithotripsy procedure cohort.
- \* With and without previous BPH surgery in the HoLEP procedure cohort.

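### The lithotripsy stone-free rate is anchored to the final Flexiva Pulse procedure and does not separate planned stages from unplanned repeats, so a retreated first-procedure failure can count as a success or drop out of the denominator.

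*Combined protocol and SAP*

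**What the plan says.** Section 11.1.2, the Synopsis and Table 6-1 define stone-free by residual fragment size, absence of obstruction and symptoms, and "no auxiliary procedures performed between the final Flexiva Pulse holmium laser lithotripsy procedure and the 1 month follow-up". Section 11.1.2.2 gives the analysis: "The proportion of subjects who achieved stone clearance at 1 month follow-up post lithotripsy procedure will be calculated". It does not say whether that procedure is the first or the last.

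Repeat procedures with the study fiber stay in the study. Section 10.6 states: "If multi-staged lithotripsy procedures are performed using the Flexiva Pulse Laser Fibers, then data will also be collected on the additional procedures". Footnote 2 of Table 10.1-1 adds: "If additional Flexiva Fiber holmium laser lithotripsy procedure is performed, complete additional procedure and discharge CRF". Follow-up visits are those "within 60 days post discharge from final Flexiva Pulse holmium laser Lithotripsy procedure" (10.8.1; 10.1 and 10.10 agree), so a further Flexiva Pulse lithotripsy restarts the follow-up window.

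Repeats without the study fiber are handled differently. If the additional lithotripsy does not use a Flexiva Pulse fiber, "then subject should be exited from the study at the time of the additional procedure" (10.10; 10.6 says the same). Section 11.3 states: "The analyses will include the available cases only unless specified otherwise".

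Section 11.3.4 plans the primary endpoints, if applicable, by the subgroup "With and without staged procedure in the Lithotripsy procedure cohort". Staged and auxiliary are not defined anywhere, and no section limits the number or timing of repeats.

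**The concern.** The auxiliary-procedure condition starts at the last Flexiva Pulse procedure. If a repeat with the study fiber is taken as the new final procedure, it cannot itself disqualify the subject. A subject left with a significant fragment after the first procedure, treated again with a Flexiva Pulse fiber and then clear, is counted with those cleared the first time.

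A subject with the same residual stone who is treated by lithotripsy with another fiber is exited. The plan does not say that this subject is scored as not stone-free. With available cases only, the subject may simply be missing.

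The SFR is a primary efficacy endpoint with no comparator, so its meaning rests entirely on its definition. Table 6-1 justifies it as the usual outcome after a ureteroscopic laser procedure, and 11.3.1.2 and 11.3.1.3 measure the secondary efficacy endpoints at the index procedure. A reader of the report could take the SFR for clearance after one procedure when it is clearance after as many Flexiva Pulse procedures as were performed.

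**Working it through.** **The plan's own figures.** There is none for the SFR. The only sample-size figures concern the SADE rate (11.1.1.2). With n = 90 and x = 90 × 0.03 = 2.7 or 90 × 0.05 = 4.5, the Clopper-Pearson widths are 8.40% and 10.23%, against 8.4% and 10.2% stated. Attrition gives 90 / (1 − 0.10) = 100. These reproduce, and the SFR definition does not affect them.

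**Route 1: repeat with a Flexiva Pulse fiber.** All inputs are assumptions:
- s1: share stone-free after the first procedure
- r: share of first-procedure failures given an unplanned Flexiva Pulse repeat
- s2: share of those then stone-free

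If an unplanned repeat counts as failure, SFR = s1. Anchored to the final procedure, SFR = s1 + (1 − s1) × r × s2. Each cell gives the result for s2 = 60% to 80%.

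| s1 | r = 10% | r = 25% | r = 50% |
|---|---|---|---|
| 60% | 62.4-63.2% | 66.0-68.0% | 72.0-76.0% |
| 70% | 71.8-72.4% | 74.5-76.0% | 79.0-82.0% |
| 80% | 81.2-81.6% | 83.0-84.0% | 86.0-88.0% |

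Smallest shift: 0.20 × 0.10 × 0.60 = 1.2 points. Largest: 0.40 × 0.50 × 0.80 = 16 points. For scale, the exact 95% interval for 70 of 100 is 60.0% to 78.8%.

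**Route 2: repeat with another fiber, exited and missing.** Let q be the share of first-procedure failures who leave this way, also assumed. The rate becomes s1 / [1 − (1 − s1) × q]. With s1 = 70%:
- q = 10%: 0.70 / 0.97 = 72.2%
- q = 25%: 0.70 / 0.925 = 75.7%

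**Both routes together**, with s1 = 70%, r = 25% and s2 = 70%: the numerator is 0.70 + 0.30 × 0.25 × 0.70 = 0.7525.
- q = 10%: 0.7525 / 0.97 = 77.6%
- q = 25%: 0.7525 / 0.925 = 81.4%

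**What the subgroup shows.** Suppose 15 of 100 subjects have a repeat and 80% are stone-free in both groups. The overall rate is 80/100.
- If staged means any repeat, the table shows 68/85 and 12/15. A reader can recover 68 of 100 cleared without a repeat, but cannot tell how many of the 15 were planned.
- If staged means planned only, unplanned repeats sit in the non-staged group and their successes stay in its rate.

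**The case against.** The strongest reply is that this is a choice of estimand, openly made. The word final appears in all three statements of the endpoint and matches the follow-up clock. Clearance after completed treatment is a legitimate target in a single-arm, standard-of-care registry, and a planned second stage is not a failed first treatment. Section 11.1.2.1 makes the endpoints descriptive, so no test, threshold or sample size depends on the SFR. All of this stands. It argues for keeping the final-anchored rate, not for leaving planned stages and rescue repeats merged within it.

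Three stronger readings are tempting, and the documents do not support them:
- A reader might infer that scoring turns on the brand of the second fiber, with a non-Flexiva repeat scored as a failure. The stated rule for such a repeat is study exit. How the subject is then scored is left open.
- A reader might infer that the planned outputs conceal the effect entirely. If staged means any repeat, the subgroup counts reveal the 68 of 100 in the example above. Only the planned/unplanned split stays hidden.
- A reader might treat it as settled that an unplanned Flexiva Pulse repeat resets the endpoint. That is the natural reading, but with auxiliary undefined the text permits it rather than states it.

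**Conclusion.** The point holds as a gap in definition and a cheap improvement. It does not make the endpoint invalid. As written, a first-procedure failure that is retreated with a Flexiva Pulse fiber and clears can be scored stone-free, and one retreated by lithotripsy with another fiber may drop out. For such subjects both routes can only raise the rate. It would be too strong to say that failed first treatments in general become successes: a repeat that leaves significant fragments is still a failure, and planned stages are not failures.

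The size is unknown. The range of about 1 to 16 points for the first route rests wholly on the assumed clearance and retreatment shares. The second route would add to it by an amount that depends on how many subjects are exited and how they are handled. Sample size and error rates are unaffected.

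**What to change.** - Keep the final-anchored SFR in 11.1.2, the Synopsis and Table 6-1, labelled as clearance after completed Flexiva Pulse treatment.
- Report beside it an SFR anchored to the index procedure. Any further stone procedure, with any fiber or method, up to the 1 month follow-up imaging counts as not stone-free unless it was recorded at the index procedure as a planned stage.
- In both figures, keep subjects exited for a lithotripsy without a Flexiva Pulse fiber in the denominator as not stone-free, as a stated exception to the available-case rule in 11.3.
- Record planned stage yes/no on the index procedure CRF, and define staged in 11.3.4 by that field.
- Report the number of Flexiva Pulse procedures per subject.

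The cost is one CRF field, capture of the non-Flexiva repeat as the exit reason, revised wording, and a second figure somewhat lower than the first. Patient care does not change. The field should be in place before enrollment, because the intention to stage is hard to reconstruct reliably once outcomes are known.
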